- f. All AEs must be reported from the first GEN3009 dose until 30 days after the last dose. If the subject initiates new anti-lymphoma therapy within 30 days of the last dose of GEN3009, the safety follow-up visit should be performed prior to starting new anti-cancer therapy.
- g. Refer to Section [9.2.2.1](#) for imaging requirements.
- h. Only for subjects with positive serology.

Table 4 Visit Assessment Schedule for PK, Immunogenicity, Biomarkers/Pharmacodynamics, and Tumor Lysis Syndrome Surveillance Sampling – Dose Escalation

Treatment Cycle: 28-day cycle		Screening										Cycle 1 and 2									
Day	Visit window	≤ D21 prior to C1D1		1d	2d	4d	8d	9d	15d	16d	22d	23d	PK/ADA ^a /Cy/Co/I/TLS	PK ^g	PK/I/TLS	PK/ADA ^b /Cy/Co/I	PK/ADA ^b /I				
Predose (-30 minutes)	Fresh tumor biopsy or archival samples for IHC																				
End of infusion ^c (+5 minutes)			PK/Cy ^f /TLS		PK ^g /Cy ^g			PK/TLS			PK/Cy ^b		PK								
End of infusion +2 hours (± 15 minutes)			PK ^f /Cy ^f /TLS		PK ^g /Cy ^g			TLS			Cy ^b										
End of infusion +4 hours (± 30 minutes)			PK ^f /Cy ^f /Co ^f /I ^f /TLS		PK ^g /Cy ^g /Co ^g /I ^g			I ^b /TLS			Cy ^b /Co ^b /I ^b		I ^b								
End of infusion +24 hours (± 2 hours)					PK ^f /Cy ^f /I ^f /TLS				I ^b /TLS			I ^b				I ^b					
End of infusion +72 hours (± 24 hours) ^h							PK/I/TLS														

Treatment Cycle: 28-day cycle		Cycle 3				Cycle 4-9			Cycle 10 And Beyond		Unscheduled		Treatment Discontinuation Visit	
Day	Visit window	1d	8d	15d	22d	1d	15d	1d	1d	1d	1d	1d	1d	1d
Predose (-30 minutes)	PK/I/Co	PK/I/Co	PK/I/Co	PK/I/Co	PK/I/Co	PK/ADA ^d /I ^d /Co ^d	PK/I ^d /Co ^d	PK/ADA ^d /I ^d /Co ^d						
End of infusion ^c (+5 minutes)	PK	PK	PK	PK	PK	PK	PK	PK	PK	PK				
Unscheduled Visit											PK/ADA/I/Co/Cy/ TB ^e		PK/ADA	

Note: Sample collection timing may be modified during the trial based on emerging data.

PK=Pharmacokinetics (Section 9.5); ADA=anti-drug antibody (Section 9.6); Cy=cytokine (Section 9.8.3.2); Co=complement (Section 9.8.3.3);

I=immunophenotyping on peripheral blood (Section 9.8.3.1); TLS=tumor lysis syndrome (Table 31); TB=tumor biopsy (Section 9.7/9.8.2)

a. Day 1 ADA in Cycle 2 only.

b. Cycle 1 only.

c. After flush.

d. ADA and biomarker samples in even cycles only.

e. Refer to Section 9.7.

- f. Only in case of full dose on Day 1
- g. Only in case of split dose between Day 1 and Day 2.

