- e. In triplicate, 5 minutes apart (\pm 5 minutes), before GEN3009 administration and 1-2 hours (\pm 15 minutes) after administration. During Cycle 4 and for all subsequent cycles, ECGs are required at predose only. During an unscheduled visit, ECG is performed only if clinically indicated.
- f. All AEs must be reported from the first GEN3009 dose until 60 days after the last dose. If the subject initiates new anti-lymphoma therapy within 60 days of the last dose of GEN3009 and/or GEN3013, the safety follow-up visit should be performed prior to starting new anti-cancer therapy.
- g. After completion of Cycle 12, subjects who are in SD or better will have the option to continue receiving GEN3013 every 4 weeks until any discontinuation criteria is met.
- h. Refer to Section [9.2.2.1](#) for imaging requirements.
- i. Only for subjects with positive serology.
- j. Even cycles only.

Table 12 Visit Assessment Schedule for PK and ADA – Expansion GEN3009 + GEN3013 (including Safety Run-in)

Treatment Cycle: 28-day cycle	Section	Cycle 1									
		1d	2d	4d	8d	9d	15d	16d	18d	22d	23d
Predose (-30 min)	9.5, 9.6	ADA: 09 and 013 / PK: 09 only	PK: 09 only ^c		PK: 09 and 13		PK: 09 and 13			PK: 09 and 13	
Start of GEN3013 Injection +1 hour (+15 min)							PK: 13 only			PK: 13 only	
End of GEN3009 infusion ^a (+5 min)		PK: 09 only	PK: 09 only ^c		PK: 09 only		PK: 09 and 13			PK: 09 and 13	
End of GEN3009 infusion +2 hours (+1 hour)		PK: 09 only ^b	PK: 09 only ^c								
End of GEN3009 Infusion +24 hours (\pm 2 hours)			PK: 09 only ^b					PK: 13 only			PK: 13 only
End of GEN3009 Infusion +72 hours (\pm 24 hours) ^d				PK: 09 only					PK: 13 only		

Treatment Cycle: 28-day cycle	Section	Cycle 2									
		1d	2d	4d	8d	9d	15d	16d	22d	23d	
Predose (-30 min)	9.5, 9.6	ADA/PK: 09 and 13			PK: 09 and 13		PK: 09 and 13		PK: 09 and 13		
Start of GEN3013 injection +1 hour (+15 min)		PK: 13 only									
End of GEN3009 infusion +5 min ^a (+5 min)		PK: 09 and 13									
End of GEN3009 infusion +2 hours (+1 hour)		PK: 09 only									
End of GEN3009 Infusion +24 hours (\pm 6 hours)			PK: 09 and 13								
End of GEN3009 Infusion +72 hours (\pm 24 hours)				PK: 09 and 13							

Treatment Cycle: 28-day cycle	Section	Cycle 3	Cycle 4-12	Cycle 13 and Beyond	Unscheduled	Treatment Discontinuation Visit
----------------------------------	---------	---------	------------	---------------------	-------------	---------------------------------

Day		1d	8d	15d	22d	1d	1d		

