2.1.4 Summary of Clinical Trials

2.1.4.1 Clinical Trials for GEN3009

This is the first time GEN3009 is being tested in humans; no prior clinical experience of GEN3009 is available. In this FIH trial of GEN3009 in R/R B-cell NHL, as of the data cut: 11 Jun 11 2021, there were 18 subjects evaluated for dose-limiting toxicities for GEN3009 at doses ranging from [REDACTED] mg to CCI [REDACTED] mg: [REDACTED] mg (N=1), [REDACTED] mg (N=1), [REDACTED] mg (N=1), CCI [REDACTED] mg (N=4), CCI [REDACTED] mg (N=4), CCI [REDACTED] mg (N=4), and CCI [REDACTED] mg (N=3). No dose-limiting toxicity (DLT) was observed. Based on the preliminary safety, PK, biomarker, and efficacy data accumulated, the dose escalation committee (DEC) and safety committee (SC) approved to add additional dose levels (ie, CCI [REDACTED] mg and CCI [REDACTED] mg) to further assess the safety, tolerability, PK, and biomar of GEN3009 in R/R B-cell NHL.

Among the 18 subjects treated with GEN3009, the most common treatment-emergent adverse events (TEAEs) in $\geq 20\%$ of subjects treated across all dose levels include infusion-related reactions (IRRs) (61.1%); heamatlogical adverse events such as neutropenia (94.4%), leukopenia

(50.0%), lymphopenia (38.9%), thrombocytopenia (38.9%), and anemia (27.8%); and fatigue and fatigue (22.2%) and headache (22.2%). IRR is an adverse event of special interest (AESI) for GEN3009 and mostly occurred during the first infusion and was of Grade 1 or 2 in severity. IRRs are manageable with interruption of the infusion, treatment, and lowering the infusion rate upon resuming the infusion. Neutropenia events were observed in majority of subjects post-GEN3009 infusions; neutrophil counts typically recovered by the next dose of GEN3009 without any clinical consequences.

Preliminary anti-tumor activity has been observed in R/R B-cell NHL subjects with GEN3009 monotherapy including 1 CR in DLBCL at [REDACTED] mg; 1 CR in SLL, 1 CR in MZL, and 1 PR in FL at [REDACTED] mg.

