Toxicology studies in cynomolgus monkeys have shown that GEN3009 was tolerated when administered intravenously at doses 0.1, 1, 3, and 10 mg/kg. MTD was deemed as 3 mg/kg in a GLP study where monkeys received 5 weekly doses and the HNSTD was considered as 10 mg/kg. Major findings from this pivotal GLP repeated-dose toxicity study include:

- B-cell depletions in peripheral blood and lymph nodes at doses ranging from 3 to 30 mg/kg;
- Transient and reversible decrease in lymphocyte, T cell, NK cell and platelet counts at 3, 10, and 30 mg/kg;
- Minimal elevations in cytokines (eg, IL-6, IL-10, and/or MCP-1) occurring shortly after dosing and returning to baseline within 12 to 24 hours which is not indicative of a CRS;
- IRRs were observed after GEN3009 administrations;
- Clinically significant and reversible hypotension observed immediately after infusion at 30 mg/kg;

- Adverse microscopic findings in the adrenal gland at 10 or 30 mg/kg;
- All GEN3009-treated animals tested positive for ADA from Day 15.

TLS is a known risk in the treatment of hematological malignancies and prophylaxis guidelines are provided in Section 6.6.1. Premedication and management for IRRs are provided in Section 6.2. Scheduled blood collections for immunogenicity are provided in Section 9.6.

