11.1.4 Immunogenicity Analysis Set

The immunogenicity analysis set will include all subjects who receive at least 1 dose of trial drug and have a baseline and at least 1 evaluable on-treatment ADA sample.

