11.7 Immunogenicity of GEN3009/GEN3013

Immunogenicity analysis samples will be scored ADA positive or ADA negative and subsequently reported. From positive ADA samples, titer values and neutralizing antibody scores (positive or negative) will be determined and reported. ADA negative samples with drug on board above the drug tolerance limits of the ADA method will be scored inconclusive due to possible drug interference. The association between positive/non-positive ADA and PK (predose, AUC, C_{max}), major safety signals (CTCAE \geq Grade 3) and efficacy information (change in tumor size by CT scan) may be explored.

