11.11 Sample Size Calculation

Sample size for the Dose Escalation is expected to be up to 90 subjects based on simulations of the mBOIN design in order to provide adequate information for MTD estimation and the planning and design of future trials. The expected number of subjects depends on the true relationship between dose and DLT probability but is expected to lie between 30 to 40 subjects in realistic scenarios. Approximately 49 additional subjects may be recruited to DLS below the MTD where it is found relevant to further explore the PK, toxicity, and efficacy.

Table 34 shows 4 different scenarios for the probability of a subject having a DLT at the 10 DLs. For each scenario the total expected number of subjects, when following the mBOIN design, is shown in the rightmost column. The mBOIN design method behaves as intended with most subjects exposed to the DLs with DLT probability close to the target DLT rate and fewer subjects exposed in total if the toxicity is high at the lowest DLs.

Table 34 Modified BOIN Design Characteristics

Simulation Scenario		Probability of DLT, Expected Number of Subjects at Each Dose Level										Expected Number of Subjects
		1	2	3	4	5	6	7	8	9	10	
1	Prob(DLT)	0%	1%	1%	2%	3%	4%	5%	10%	20%	30%	
	Num of subjects	1.0	1.1	1.1	3.2	3.4	3.5	3.8	5.1	5.9	4.6	32.7
2	Prob(DLT)	0%	1%	1%	2%	3%	4%	5%	20%	25%	35%	
	Num of subjects	1.0	1.1	1.1	3.3	3.4	3.5	4.9	6.2	4.7	2.9	32.0
3	Prob(DLT)	0%	1%	1%	2%	3%	4%	5%	20%	40%	60%	
	Num of subjects	1.0	1.0	1.1	3.3	3.3	3.5	5.0	7.3	4.8	1.0	31.3
4	Prob(DLT)	0%	1%	1%	2%	3%	4%	5%	10%	12%	15%	
	Num of subjects	1.0	1.0	1.1	3.2	3.4	3.5	3.8	4.3	4.4	6.6	32.2

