5.2.2 Baseline values

The **baseline value** is defined to be the last non-missing value which was assessed before the first dose of investigational treatment.

- If an assessment date, but not time, is collected, and the assessment date is the same as the date of first dose of investigational treatment, that assessment will be used to derive the baseline value (if it is non-missing).
- If the assessment time is collected, and the time of the first dose of investigational treatment is collected, and the assessment date is the same as the date of first dose of investigational treatment, that assessment may only be used to derive the baseline value if the assessment time is prior or equal to the start of administration of investigational treatment.
- If multiple assessments are collected on the same day, without recorded time of assessment, the algorithm in Section 5.8(d)(iii) will be followed.

Change from baseline is defined as the post-baseline value minus the baseline value, and will be missing if the baseline value is missing.

Percent change from baseline is defined as $100^* (\text{change from baseline})/\text{baseline value}$. If the baseline value and post-baseline value are both 0, the percent change from baseline will be set to 0. If the baseline value is 0, or missing, and the post-baseline value is non-zero, the percent change from baseline will be set to missing.

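### Dose Escalation takes no ADA sample before the first dose, yet the immunogenicity set requires a baseline sample, so no escalation subject can qualify from scheduled draws

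*Protocol*

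**What the plan says.** Protocol Table 4 governs ADA sampling in Dose Escalation. Its Day 1 predose cell, in the columns covering Cycles 1 and 2, lists ADA with PK, cytokines, complement, immunophenotyping and tumor lysis samples. ADA alone carries footnote a: "Day 1 ADA in Cycle 2 only".

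Protocol Section 11.1.4 defines the immunogenicity analysis set as subjects who received trial drug and "have a baseline and at least 1 evaluable on-treatment ADA sample". SAP Section 5.2.2 defines baseline as the "last non-missing value which was assessed before the first dose of investigational treatment".

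Expansion is handled differently. Table 7 (monotherapy) schedules ADA at Cycle 1 Day 1 predose, and the same cell in Table 12 (combination) reads "ADA: 09 and 013 / PK: 09 only".

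**The concern.** The sampling schedule and the analysis-set definition cannot both be followed in Dose Escalation. The set needs a pre-dose sample that the schedule does not collect.

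The incidence of neutralizing ADA to GEN3009 is a secondary endpoint of this part (Protocol Table 17). SAP Section 11.8 calls a subject ADA-positive on any single positive result. That status is then used to split adverse event tables (SAP 11.1), tumor size summaries (SAP 10.3.2), and concentrations and PK parameters (SAP 13.1 and 13.2). Without a baseline, a subject with pre-existing reactivity and one who developed antibodies on treatment fall into the same group. Expansion will have baselines, so ADA results from the two parts will not mean the same thing when read side by side.

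**Working it through.** The plan states no figure to reproduce. The check compares the schedule with the definition, then counts the subjects affected.

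**1. Every scheduled escalation ADA sample**

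| Source | Time point | Before first dose? |
|---|---|---|
| Table 4, Screening | Tumor tissue only, no ADA | – |
| Table 2, Screening and Cycle 1 | No ADA listed | – |
| Table 4, footnote a | Cycle 2 Day 1 predose | No |
| Table 4, footnote b | Cycle 1 Days 15 and 22 predose | No |
| Table 4, footnote d | Day 1 of even cycles from Cycle 4 | No |
| Table 4 and Section 9.6 | Treatment discontinuation or final visit | No |

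Scheduled ADA samples before the first dose: 0 per subject. Table 4 also allows ADA at unscheduled visits, but none is planned before dosing. Days 15 and 22 are read from the column order of a table that did not extract cleanly. The result does not depend on that reading, because footnote a is explicit and the Screening column holds no ADA.

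**2. Could an early on-treatment sample serve as baseline?**

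Not under SAP 5.2.2, because the Day 1 and Day 8 doses precede Day 15. Two further points support this without being needed for it. In the monkey study, "All GEN3009-treated animals tested positive for ADA from Day 15". Under Protocol Section 11.7, "ADA negative samples with drug on board above the drug tolerance limits of the ADA method will be scored inconclusive".

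**3. Subjects meeting Section 11.1.4 from scheduled samples**

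The set needs a baseline and an on-treatment sample. With no scheduled baseline, 0 escalation subjects qualify.

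**4. How many can still be given a baseline**

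At the 11 Jun 2021 data cut (Protocol Section 2.1.4.1), "there were 18 subjects evaluated for dose-limiting toxicities for GEN3009". By dose level: 1 + 1 + 1 + 4 + 4 + 4 + 3 = 18 over seven levels. Section 4.3.1 adds three higher levels, taken here as dose levels 8 to 10 of Table 34.

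| Table 34 scenario | Expected at levels 8 + 9 + 10 | Total with the 18 | Share not yet dosed |
|---|---|---|---|
| 1 | 5.1 + 5.9 + 4.6 = 15.6 | 33.6 | 15.6/33.6 = 46.4% |
| 2 | 6.2 + 4.7 + 2.9 = 13.8 | 31.8 | 13.8/31.8 = 43.4% |
| 3 | 7.3 + 4.8 + 1.0 = 13.1 | 31.1 | 13.1/31.1 = 42.1% |
| 4 | 4.3 + 4.4 + 6.6 = 15.3 | 33.3 | 15.3/33.3 = 45.9% |

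These totals agree with Protocol Section 11.11, where the expected number "is expected to lie between 30 to 40 subjects in realistic scenarios".

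Section 4.1.1.1 also allows up to 49 parallel subjects. If all 49 were still to come, the share would be (13.1 + 49)/(31.1 + 49) = 62.1/80.1 = 77.5% in scenario 3 and (15.6 + 49)/(33.6 + 49) = 64.6/82.6 = 78.2% in scenario 1.

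**The case against.** The best defence is that no planned analysis stops. Section 11.7 never names the immunogenicity set. The SAP, written to protocol version 4.0, does not define one, and its ADA status rule needs only one positive or negative result. Neither document defines treatment-emergent ADA. This stands: ADA can still be reported, and the loss is one of interpretation, mainly for ADA-positive subjects. But the current protocol does define the set, so an updated SAP will have to deal with the conflict.

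Several smaller points also stand. SAP 5.5 lists baseline ADA only as an optional covariate, and SAP 5.6 confines exploratory subgroup use to Expansion, so that consequence is minor. The two parts are reported separately and no pooling of ADA is planned. The monkey finding may not carry over to patients, and the assay's drug tolerance limit is not given. The Table 34 counts are not conditioned on the absence of DLTs so far, and the data cut precedes the amendment of 9 Jul 2021, so some of the 13 to 16 may already have been dosed.

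Table 4 notes that sample timing may be modified during the trial. That may ease the correction, but it schedules no baseline sample.

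**Conclusion.** The concern holds. As scheduled, the protocol-defined immunogenicity set is empty in Dose Escalation, and ADA there can be described only as any-positive prevalence. This affects a descriptive secondary endpoint, not dose selection or a primary analysis, so it should be corrected but does not threaten the trial.

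About 13 to 16 design subjects, or 42 to 46% of roughly 31 to 34, could still gain a baseline, rising to about 78% if all 49 parallel subjects are enrolled later. This assumes that nobody was dosed after the data cut and that levels 8 to 10 are all opened; the number is smaller if the optional intermediate level is skipped. A baseline not drawn before the first dose cannot be collected afterwards, so timing matters.

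**What to change.** 1. **Protocol Table 4, footnote a:** remove the Cycle 2 restriction so that ADA is drawn at the Cycle 1 Day 1 predose visit for every escalation subject not yet dosed, as in Tables 7 and 12.
2. **Protocol Section 11.1.4:** admit already-dosed escalation subjects who have an evaluable post-dose sample, and report them separately as prevalence.
3. **SAP Section 11.8, at the update to the current protocol:** add the immunogenicity set and define treatment-emergent ADA relative to baseline where a baseline exists.
4. **Subjects already dosed:** check whether Cycle 1 Day 1 predose serum from the complement (CH50) draw was kept and can be tested; the documents do not say. Predose PK plasma also exists, and Section 9.5 allows some further use, but ADA is assayed in serum, so its suitability is unknown.

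The cost is one serum tube at a draw already being made and about 13 to 16 extra ADA assays, plus one for each parallel subject (up to 49). The text changes are short. If the Table 4 timing note does not cover an added time point, the change needs a formal amendment with the approvals in Section 14.1, and could be included in the next one provided that is in place before further escalation subjects are dosed.

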- g. In triplicate, 5 minutes (\pm 5 minutes) apart, before GEN3009 administration and 1-2 hours (\pm 15 minutes) after administration.
- h. All AEs must be reported from the first GEN3009 dose until 30 days after the last dose (refer to Table 6 for details on the safety follow-up visit). Medical conditions that occur after the ICF is signed and prior to first GEN3009 dose should only be reported as AEs if they were assessed by the investigator to be caused by a protocol-mandated procedure (ie, tumor biopsy and/or CT scan), including washout or discontinuation of prior medications.
- i. MRI/CT scan of the brain is mandatory during screening within 21 days of C1D1. Lumbar puncture is required only if clinically indicated and required within 21 days of C1D1.
- j. HIV testing is required at screening only if required per local health authorities or institutional standards
- k. At dose levels \geq [REDACTED] mg, the first dose of GEN3009 can be split into 2 consecutive days (ie, [REDACTED] mg at C1D1 and remaining amount at C1D2) after approval of the sponsor's medical monitor.

Table 11 Visit Assessment Schedule from Cycle 2 and Beyond – Expansion GEN3009 + GEN3013 (including Safety Run-in)

Treatment Cycle 28-day cycle	Section	Cycle 2-3						Cycle 4 -12	Cycle 13 and Beyond	Unscheduled	Treatment Discontinuation Visit ^a	Safety Follow- up Visit ^a	Survival Follow- up Visit ^b
Day		1d	4d	8d	11d	15d	22d	1d	1d	--	As soon as possible after withdrawn from treatment	60 days after last dose	Every 12 weeks after last dose
Visit Window		±2d		±2d		±2d	±2d	±2d	+7d		+7d	+14d	±14d
Body Weight	9.3.1	X		X		X	X	X	X	X	X		
Physical Examination (including lymph node assessment) ^c	9.3.1	X						X	X	X	X		
Neurotoxicity Syndrome Assessment	9.3.1.1	X		X		X	X	X	X	X	X		
Vital Signs	9.3.2	X ^d		X ^d		X ^d	X ^d	X ^d	X	X	X		
ECG (in triplicate)	9.3.3	X ^e		X ^e		X ^e	X ^e	X ^e		X ^e	X		
ECOG Performance Status	9.3.4	X						X	X	X	X		
Constitutional Symptoms	9.3.5	X						X	X	X	X		
Adverse Events ^f	10	X	X	X	X	X	X	X	X	X	X	X	
Concomitant Medication and Procedures	9.1.4	X	X	X	X	X	X	X	X	X	X	X	
Premedication & CRS Prophylaxis	6.2	X		X		X	X	X	X				
GEN3009 Administration	6.4.2	X		X		X	X	X					
GEN3013 Administration	6.4.2	X		X		X	X	X	X ^g				
New Anti-cancer Treatment												X	X
Survival Status	9.3.6											X	X
EFFICACY ASSESSMENTS													

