Treatment Cycle 28-day cycle	Section	Cycle 2-3							Cycle 4 -12	Cycle 13 and Beyond	Unscheduled	Treatment Discontinuation Visit ^a	Safety Follow- up Visit ^a	Survival Follow- up Visit ^b
Day		1d	4d	8d	11d	15d	22d	1d	1d	--	As soon as possible after withdrawn from treatment	60 days after last dose	Every 12 weeks after last dose	
Visit Window		±2d		±2d		±2d	±2d	±2d	+7d		+7d	+14d	±14d	
FDG- PET/CT/MRI	9.2.2.1	X ^h												
Lymphoma with Bone Marrow Involvement: Unilateral bone marrow biopsy and aspirate	9.2.2.2	X (at time of CR and clinically indicated)												
LABORATORY ASSESSMENTS														
Hematology: Complete blood count with differential ^c	9.4.1	X	X	X	X	X	X	X	X	X	X	X		
biochemistry	9.4.1	X	X	X	X	X	X	X	X	X	X	X		
Coagulation	9.4.1	X	X	X	X	X	X	X	X	X	X	X		
Immunoglobulins (IgA, IgE, IgG, IgM)	9.4.1	X						X	X			X		
Urinalysis	9.4.1	X						X	X	X	X			
Pregnancy Test (either urine or serum)	9.4.1	X						X	X	X	X	X	X	
Hepatitis B and C Serology	9.4.1										X ⁱ			

- Subjects discontinuing from treatment for any reason will have a safety follow-up visit 60 days after the last dose of GEN3009 and/or GEN3013. If the subject initiates new anti-lymphoma therapy within 60 days of the last dose of GEN3009 and/or GEN3013, the safety follow-up visit should be performed prior to starting new anti-cancer therapy.
- Subjects will enter the survival follow-up after completion of the safety follow-up or if new anti-cancer treatment has been started. Survival follow-up contact may be performed as a telephone call, email, or on-site visit.
- Physical examination may be performed within 1 day prior to GEN3009 dosing. Refer to Section 9.4.1 for timing of laboratory assessments.
- On dosing days, vital signs are performed predose and postdose, and more frequently at the discretion of the investigator. If the subject has stable vital signs and no other issues, the subject may be discharged from the clinic after all assessments are completed as required by protocol. Subjects must be instructed to contact the investigator should signs or symptoms of infusion-related reactions and/or CRS (eg, fever, lightheadedness, shortness of breath, etc.) occur following discharge from the clinic.

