7.4.2.2 GEN3013 Dose Modification Rules

Dose reduction is not allowed for GEN3013 on an individual subject level in this trial. Refer to Section [4.3](#) for dosing rationale.

If a dose is delayed more than 6 weeks, the subject should be asked to perform an unscheduled visit for collection of AEs, concomitant medications, laboratory values (including hematology, biochemistry, and coagulation values), and a limited physical examination (as clinically indicated) after consultation with the sponsor's medical monitor.

A repriming cycle is necessary if dose is delayed at certain time points, as described below. A repriming cycle consists of a weekly schedule of a priming dose, intermediate dose, and 2 full doses. Refer to [Table 15](#) for the repriming cycle Visit Assessment Schedule.

A repriming cycle should occur:

- For the second GEN3013 full dose onward (ie, C2D1), if the interval between the previous dose of GEN3013 and next planned dose exceeds 6 weeks.

During the repriming cycle, CRS prophylaxis must be resumed with 3 consecutive days of corticosteroids beginning at each GEN3013 dose, until at least 1 full dose of GEN3013 is administered without subsequent occurrence of CRS Grade ≥ 2 (see Section [6.2.2](#)).

Once the full repriming cycle is completed, the subject should resume treatment with Day 1 of the next planned cycle (subsequent to the cycle during which the dosing was delayed). For example, if the subject experiences a 7-week delay after C3D1, the subject should receive a repriming cycle, then continue treatment at C4D1. GEN3009 dose will continue as scheduled.

If GEN3013 dose is delayed, withheld, or discontinued during the combination treatment period, GEN3009 can be continued if approved by the sponsor's medical monitor.

Refer to Section [7.4.3](#) for information about dose modifications due to AEs.

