8 DISCONTINUATION, FOLLOW-UP AND COMPLETION

8.1 Discontinuation of Treatment

A subject's trial drug may be discontinued for any of the following reasons:

- Unacceptable AE requiring treatment discontinuation (refer to Section 7)*
- Subject non-compliance
- Sponsor decision
- Subject request to discontinue treatment*
- Pregnancy
- Clinical progression*
- Disease progression according to response criteria
- Other

*Imaging should continue to be performed until evidence of radiographic disease progression despite treatment discontinuation. When a subject discontinues trial drug, they are to remain on trial and are to be followed until death, initiation of subsequent therapy, or any other reason listed in Section 8.2.

Subjects should be examined regularly according to the protocol schedule, or more frequently, as needed. If the decision to discontinue trial drug treatment occurs around the time of the next planned treatment administration visit, the assessment schedule for the treatment discontinuation visit should be followed. Subjects should be followed for safety within 30 days of the last administration of trial drug in GEN3009 monotherapy cohorts and 60 days of the last administration of trial drug in GEN3009 + GEN3013 combination cohort

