8.3 Safety Follow-up Visit

Subjects discontinuing from treatment for any reason will have a safety follow-up visit 30 days after the last dose of trial drug in GEN3009 monotherapy cohorts and 60 days after the last administration of trial drug in the GEN3009 + GEN3013 combination cohort. If the subject initiates new anti-lymphoma therapy after the discontinuation of treatment, the safety follow-up visit should be performed prior to starting new anti-cancer therapy. Once the safety follow-up visit is completed, the subject will move into survival status follow up (refer to Section [9.3.6](#)).

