9.1.4 Concomitant Medication and Procedures

Any medication or therapy (including OTC or prescription medicines, vitamins, and/or herbal supplements, vaccinations, and blood transfusions) other than GEN3009 is considered concomitant medication and must be recorded. Relevant prior concomitant medication administered and/or procedures during the trial must be recorded from <21 days prior to the first dose of GEN3009 and up to 30 days after the last dose of GEN3009 in the monotherapy arms and 60 days after the last dose of GEN3009 + GEN3013 in the combination arm. The subject must be instructed to notify the investigational site about any new medications he or she takes after the start of the trial drug. The medical monitor should be contacted if there are any questions regarding concomitant or prior therapy/procedures.

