10.2 Adverse Event Reporting

All AEs, whether serious or nonserious (see definition in section [10.1.2](#)), will be documented from the first dose of GEN3009 and/or GEN3013 (GEN3009 + GEN3013 cohort only) until 30 days after the last GEN3009 and 60 days after the last dose of GEN3013, subject withdrew consent, subject started new anti-cancer treatment, or the subject died, whichever comes first. Refer to the electronic case report form (eCRF) completion guidelines for additional information on reporting and stepwise guidance.

Medical conditions (signs, symptoms, and diagnoses) that occur after the ICF is signed and prior to the first GEN3009 and/or GEN3013 dose should only be reported as AEs if they were assessed by the investigator to be caused by a protocol-mandated procedure (ie, tumor biopsy and/or CT scan), including washout or discontinuation of prior medications.

The investigator will use the CTCAE Version 5.0 ([NCI, 2017](#)) to describe the intensity of AEs, except for TLS (refer to [Appendix 4](#)), CRS (refer to [Appendix 13](#)) and ICANS (refer to [Appendix 14](#)). Changes in intensity of an ongoing AE should be assessed at each visit or more frequent if deemed necessary and must be reported.

SAEs still ongoing after the safety follow-up visit(s) should be followed on a regular basis according to the investigator’s clinical judgment until the event has been resolved or until the investigator assesses it as chronic and all queries have been resolved. Only SAEs judged by the investigator as related to GEN3009 (all cohorts) and/or GEN3013 (the combination cohort only) should be reported after the safety follow-up visit.

The investigator must assess whether or not the event is related to the trial drug. The relationship is to be judged using the following terms:

- Related
- Not related

If the relationship changes over time, the last judgment by the investigator should be reported. Relatedness has to be assessed and reported from the first time the event is being reported.

A suspected adverse reaction is one in which there is a reasonable possibility that the trial drug caused the AE; this means there is evidence to suggest a causal relationship between the trial drug and the AE (ie, considered related).

Note:

- Final assessment of AEs must be performed by a medically qualified person, ie, a medical doctor.

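### For the GEN3009 + GEN3013 cohort the protocol ends AE reporting at 30 days (Table 10), at 60 days (Table 11), and by an unresolved two-clock rule (Section 10.2)

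*Protocol*

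**What the plan says.** Tables 10 and 11 of the protocol both cover the GEN3009 + GEN3013 expansion cohort, including the safety run-in. Table 10 is for screening and Cycle 1, and Table 11 is for Cycle 2 onward.

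- **Table 10, footnote h:** "All AEs must be reported from the first GEN3009 dose until 30 days after the last dose (refer to Table 6". Table 6 is the monotherapy schedule, with its safety visit at 30 days.
- **Table 11, footnote f:** "All AEs must be reported from the first GEN3009 dose until 60 days after the last dose".
- **Section 10.2:** AEs are documented "until 30 days after the last GEN3009 and 60 days after the last dose of GEN3013". The sentence then lists consent withdrawal, new anti-cancer treatment and death, and closes by taking the earliest.

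The neighbouring rules for this cohort use 60 days:

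- **Table 11, footnote a:** subjects "will have a safety follow-up visit 60 days after the last dose of GEN3009 and/or GEN3013".
- **Section 8.1:** follow-up for safety within "60 days of the last administration of trial drug in GEN3009 + GEN3013 combination cohort".
- **Section 8.3:** the safety visit is "60 days after the last administration of trial drug in the GEN3009 + GEN3013 combination cohort".
- **Section 9.1.4:** concomitant medication is recorded until "60 days after the last dose of GEN3009 + GEN3013 in the combination arm".

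The SAP does not settle the matter. It is based on protocol version 4.0 (Amendment 2), which has no combination cohort. SAP Section 11.1 collects AEs for 30 days after the last GEN3009 dose, and SAP Section 5.8 ends the on-treatment period 28 days after the last dose.

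**The concern.** One subject cannot have two different ends of AE reporting. Table 10 schedules Cycle 1 only, but that does not explain the difference. Each footnote states the whole window, from the first GEN3009 dose to a fixed time after the last dose.

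The boundary has practical force. Section 10.4.1 requires SAEs to reach the sponsor within 24 hours if they occur in the safety reporting period, and these are the passages that define that period. After the safety follow-up visit, Section 10.2 asks only for SAEs judged related. Between day 30 and day 60, whether a site must report a non-serious AE or an unrelated SAE therefore depends on which page it follows. AE, AESI and SAE frequency and severity is a primary endpoint of the run-in (Table 19) and a secondary endpoint of the combination expansion (Table 20).

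Section 10.2 adds a second difficulty because the two drugs can stop at different times. Under Section 7.4.2.2, if GEN3013 is delayed, withheld or discontinued, "GEN3009 can be continued if approved by the sponsor's medical monitor". In the other direction, GEN3009 ends by Cycle 12 while GEN3013 may go on (Section 4.1).

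**Working it through.** The plan states no figure to reproduce. The check compares day counts under each text.

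**Notation.** N is the study day of the last GEN3009 dose and T that of the last GEN3013 dose. Let L = max(N, T).

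| Text | End of AE reporting |
|---|---|
| Table 10, footnote h | L + 30 |
| Table 11, footnote f | L + 60 |
| Section 10.2, later clock governs | max(N + 30, T + 60) |
| Section 10.2, earlier clock governs | min(N + 30, T + 60) |

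Footnotes f and h do not name the drug whose last dose counts. I take it as the last dose of either drug, in line with Section 8.3.

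**Table 10 against Table 11.** (L + 60) − (L + 30) = 30 days, for any subject.

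**Section 10.2, later clock, against Table 11.**

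- If T ≥ N, the end is T + 60 in both, so the shortfall is 0.
- If N > T, the shortfall is (N + 60) − max(N + 30, T + 60) = min(30, N − T).
- If no GEN3013 was given, only the first clock exists and the shortfall is 30 days.

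**Cases.**

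1. *Both drugs last given on day D.* Table 10 gives D + 30 and Table 11 gives D + 60. Section 10.2 gives D + 60 (later clock) or D + 30 (earlier clock).
2. *Subject stops after the Cycle 1 Day 1 lead-in, before any GEN3013.* Table 10 and Section 10.2 give 30 days after that dose. Table 11 gives 60.
3. *GEN3009 outlasts GEN3013 by one week.* With the later clock the shortfall is min(30, 7) = 7 days.
4. *GEN3013 stops after Cycle 1 Day 22 and GEN3009 continues to Cycle 12 Day 1.* N = 11 × 28 + 1 = 309 and T = 22. The two clocks in Section 10.2 end on days 339 (309 + 30) and 82 (22 + 60), so the later one gives day 339. Table 10 also gives day 339. Table 11 gives 309 + 60 = day 369. The shortfall is min(30, 287) = 30 days.
5. *GEN3009 ends at Cycle 12 Day 1 (day 309) and GEN3013 continues every 4 weeks.* With the earlier clock, reporting ends on day 339. The Cycle 14 Day 1 dose of GEN3013 falls on day 13 × 28 + 1 = 365, after reporting has closed.

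**The case against.** The best case against the point is that the protocol's intention is clear. Table 10 has no discontinuation or follow-up column. Those columns are in Table 11, which sets the safety visit at 60 days and marks AE collection there. Section 8.2 sends subjects who leave the trial to Tables 3, 6 and 11, not to Table 10. Sections 8.1, 8.3 and 9.1.4 all use 60 days. AEs are to be assessed at every visit (Section 10.2), so the day-60 visit should pick up earlier events, and related SAEs stay reportable afterwards (Sections 10.2 and 10.4.2). On its natural reading, Section 10.2 needs both clocks to run out, which gives 60 days whenever GEN3013 is given last or on the same day. That is the planned course from Cycle 1 Day 8.

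Most of this stands, and it limits the size of the problem. Footnote h looks like a carry-over from a monotherapy table, although that is an inference. It does not remove the conflict: footnote h is an explicit instruction, and Section 10.2, the section on AE reporting, does not say how its clocks combine.

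A reader might infer three stronger things, which the documents do not support.

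- *About half of late AEs would be missed.* This needs events spread evenly over the 60 days and every site following Table 10. The documents give no data on either.
- *AE rates would not be comparable between the run-in dose levels.* The same footnotes apply to both levels, and nothing in the text would make them act differently by dose.
- *The run-in's primary AE frequencies would be biased downward.* Section 11.4.1.1.1 limits AE summary tables to on-treatment events; later events are listed and flagged. The only definition of that period, in the version 4.0 SAP, ends at 28 days, before either window closes.

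**Conclusion.** The inconsistency is real and should be corrected. For the combination cohort the end of AE reporting is given as 30 days, as 60 days, and as a two-clock rule with no stated way to combine the clocks.

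A site following Table 10 could stop reporting non-serious AEs and unrelated SAEs up to 30 days before the 60-day visit. Under Section 10.2 with the later clock, the shortfall is 30 days if no GEN3013 was given, min(30, gap in days) if GEN3009 outlasts GEN3013, and zero otherwise. With the earlier clock, reporting could end during GEN3013 treatment. That is presumably not intended, but the wording does not exclude it.

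The effect falls mainly on AE listings, SAE and AESI reporting and DMC review. The DLT endpoint uses the first 28 days and is unaffected. Summary tables limited to on-treatment AEs are also unaffected, unless an updated SAP widens that period for this cohort. The finding is that the texts disagree; the documents do not show how any site reads them, so no count of lost events can be given.

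**What to change.** Reconcile the passages to the window the protocol already uses elsewhere for this cohort.

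1. **Table 10, footnote h:** change 30 days to 60 days, and refer to Table 11 instead of Table 6.
2. **Section 10.2:** state the rule by cohort. For monotherapy, 30 days after the last GEN3009 dose. For the combination, 60 days after the last dose of either drug, whichever is later. Keep the existing stops for consent withdrawal, new anti-cancer therapy and death.

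When the SAP is updated to include the combination cohort, it should state the on-treatment period for that cohort, so that it is clear which of these events enter summaries and which are only listed.

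The cost is one footnote and one sentence in an amendment, and slightly more AE data to record. The 60-day visit with AE collection is already scheduled, so no new visit is needed. Only data collection changes.
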